3.4.2 Secondary Endpoints

The incidence, duration, and number of courses of CMV anti-viral therapy through 12 months after transplant will be summarized descriptively for the mITT Population, as will the following:

- Incidence and time to clinically significant CMV infection, CMV disease, and CMV syndrome
- Incidence and time to CMV viremia requiring anti-viral therapy
- Incidence and duration (in days) of anti-CMV therapy courses (at therapeutic doses) required
- Incidence and time to quantifiable CMV DNAemia, peak CMV DNAemia level, and duration of CMV DNAemia above the limit of quantitation
- Incidence and time to graft failure and organ rejection

The post-transplant CMV syndrome, disease, infection, infection requiring anti-viral therapy, post-transplant anti-viral therapy use will also be summarized in separate tables by syndrome and disease type according to the dose of vaccines or placebos received and for all post-transplant patients regardless of dose of medications.

3.4.2.1 Secondary Endpoint Definitions

- CMV infection is defined as quantifiable local CMV PCR test results above the lower limit of quantification (LLOQ).
- CMV syndrome is defined as CMV infection with at least one syndrome symptom present.
- CMV syndrome disease is defined as CMV infection with (CMV syndrome OR at least one end-organ disease category present).

- CMV infection requiring anti-viral therapy is defined as the triggered start of anti-virals as entered on Local CMV PCR results CRF.
- Time to infection is defined as the date of the first quantifiable result above LLOQ – transplant date.
- Duration above LLOQ is the number of consecutive days with a quantifiable result above LLOQ, starting with the first such value.
- Anti-viral therapy use is defined as the recorded use of flagged anti-viral therapies on the concomitant medication CRF following the triggered start of anti-virals as entered on the Local CMV PCR results CRF.
- Time to anti-viral therapy use is defined as the date of the first post-transplant anti-viral use – transplant date.
- Duration of anti-viral therapy use is the total number of days of recorded post-transplant anti-viral use.
- Number of anti-viral therapy courses is the sum of unique recorded post-transplant anti-viral entries on the concomitant medication CRF.
- Time to rejection is defined as first date of biopsy with rejection recorded – transplant date.

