The patient will complete and conclude the study on whichever day of the study one of the following events first occurs:

- When the patient completes the study follow-up (12 months post-transplant).
- If for some reason kidney transplant has not occurred by 12 months after the first dose of study drug (HB-101 or placebo).
- If the patient experiences graft failure requiring removal of the transplanted organ or returns to dialysis.
- If the patient is withdrawn or withdraws from the study.
- If the patient is lost to follow-up.
- If the patient dies.

The total duration of the study for each patient participating in the study will be approximately 15 months.

The dosing schedule relative to transplantation is listed in Table 1.

Study drug is defined as either HB-101 or placebo.

Table 1 Timing of Kidney Transplant vs. Study Drug (HB-101 or Placebo) Injection, Where Day 0 is the Day of First Dose of Study Drug

Timing of Kidney Transplant	Number of Injections Planned	Timing of Study Drug Injection
Prior to Day 34	1*	Day 0
Between Day 35 and Day 62	2	Day 0 and Day 28**
Between Day 63 and Day 90 or Between Day 91 and Day 120	3	Day 0, Day 28**, and Day 56** or Day 84**
*Patients who received only 1 dose of study drug will be excluded from the mITT Population for efficacy analysis. **After Day 0 dose administration, a timeframe of ± 7 days from scheduled day of dosing is allowed. mITT = modified Intent-to-Treat; Day 0 = day of first dose of study drug; Day 28 = 28 days after the first dose of study drug; Day 34 = 34 days after the first dose of study drug; Day 35 = 35 days after the first dose of study drug; Day 56 = 56 days after the first dose of study drug; Day 62 = 62 days after the first dose of study drug; Day 63 = 63 days after the first dose of study drug; Day 84 = 84 days after the first dose of study drug; Day 90 = 90 days after the first dose of study drug; Day 91 = 91 days after the first dose of study drug; Day 120 = 120 days after the first dose of study drug.		

In brief, it is the intent of this study to administer up to 3 doses of study drug (HB-101 or placebo) prior to transplantation and within proximity to the time of transplantation. However, 2 doses of study drug before transplant will be sufficient for the patients to be included in the efficacy analyses if a third dose of study drug is not feasible due to transplantation timelines. Patients will not receive study drug after transplantation.

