3.1.3 Summary Statistics

Continuous variables will be summarized by using the number of non-missing observations, arithmetic mean, standard deviation, median, minimum, and maximum values as descriptive statistics. Categorical variables will be summarized by using the frequency count and the percentage of patients in each category as descriptive statistics. All data will also be listed.

Within each population, results will be presented according to treatment arm and total for Groups 1 and 2 and open-label HB-101 for Group 3 and total for all the three groups unless specified otherwise. Results from Groups 1 and 2 and results from Group 3 will be displayed in separate outputs unless specified otherwise.

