3.1.5 Handling of Dropouts and Missing Data

In general, data will be analyzed and presented as observed and will not be imputed for the analysis of efficacy and safety.

In case the start and end dates for adverse events and concomitant medications/procedures are missing or incomplete, the missing component(s) will be assumed as the most conservative value possible. For example, Adverse Events (AEs) with missing start dates, but with stop dates either overlapping into the treatment period or missing, will be counted as treatment-emergent, taking the worst-case approach. When partial dates are present in the data, both a partial start date and/or a partial stop date will be evaluated to determine whether it can be conclusively established that the AE started prior to the start of study treatment or ended prior to the start of study treatment. If the above cannot be conclusively established based on the partial and/or present dates, then the AE will be considered as treatment-emergent. Actual data values as they appear in the original case report forms (CRFs) will be presented in the data listings.

If a medication has incomplete start or stop dates, dates will be imputed to determine whether a medication should be considered prior or concomitant. If a medication start date is incomplete, the first day of the month will be imputed for missing day and January will be imputed for missing month. If a medication stop date is incomplete, the last day of the month will be imputed for missing day and December will be imputed for missing month. Incomplete start and stop dates will be listed as collected without imputation.

3.1.6 *COVID-19 pandemic*

The COVID-19 pandemic may impact the conduct of the study from different aspects including quarantines, site closures, travel limitations, interruptions to the supply chain for the investigational product, or other considerations if site personnel or trial patients become infected with COVID-19. Study procedures affected by the COVID-19 pandemic are recorded, as are reasons for study discontinuation/screen failure, protocol deviations, and adverse events. All such data will be listed, and any summaries of this data are mentioned below.

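### The 'time to' secondary endpoints have values only for patients with the event, and the SAP gives no censoring rule or time-to-event summary although follow-up can end before 12 months

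*SAP*

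**What the plan says.** Section 3.4.2 lists incidence and time to clinically significant CMV infection, CMV disease and syndrome, viremia needing anti-viral therapy, quantifiable DNAemia, graft failure and rejection. All are summarised descriptively in the mITT Population.

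Section 3.4.2.1 then defines the times that it names:

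- Infection: "Time to infection is defined as the date of the first quantifiable result above LLOQ", minus the transplant date.
- Rejection: "Time to rejection is defined as first date of biopsy with rejection recorded", minus the transplant date.
- Anti-viral use: date of first post-transplant use minus the transplant date.

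The general rules that apply to these variables are:

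- Section 3.1.3: "Continuous variables will be summarized by using the number of non-missing observations, arithmetic mean, standard deviation, median, minimum, and maximum values".
- Section 3.1.5: "In general, data will be analyzed and presented as observed and will not be imputed for the analysis of efficacy and safety".

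Section 2.2.1 plans follow-up to 12 months after transplant, but ends it earlier for graft failure (organ removal or return to dialysis), death, and these two cases: "If the patient is withdrawn or withdraws from the study"; "If the patient is lost to follow-up".

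On duration, section 3.4.2.1 says: "Duration above LLOQ is the number of consecutive days with a quantifiable result above LLOQ, starting with the first such value". For anti-viral treatment it says: "Duration of anti-viral therapy use is the total number of days of recorded post-transplant anti-viral use".

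Section 2.2.4 gives one use of the efficacy data: point estimates of clinical efficacy endpoints, with clinically significant CMV infection named, to design and power Phase 3.

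**The concern.** A time defined as an event date minus the transplant date does not exist for a patient who stays event-free. Averaging the times that do exist describes when events happened among those who had them. It reflects prevention poorly, because a prevented event leaves the calculation instead of lengthening it.

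The crude proportion reported beside it counts a patient who left at month 2 without an event as event-free for the whole year. Where patients withdraw or are lost, this understates the 12-month risk. Where death precludes the event, the patient truly cannot have it later, and the proportion is not biased in that way.

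What is at stake is the absolute 12-month risk and the timing of clinically significant CMV infection, since Phase 3 is to be planned from them. The primary safety and immunogenicity conclusions are not touched.

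**Working it through.** **Text check.** Sections 2.2.1, 3.1.3 to 3.1.5, 3.4.2, 3.4.2.1, 4.1 and 5 contain no censoring date, no Kaplan-Meier or cumulative incidence estimate, and no handling of death or graft loss for these endpoints. Section 4.1 carries the same methods into any interim analysis. The SAP states no figure for these endpoints, so there is none to reproduce.

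**Assumptions (none is in the SAP).** The 12-month risk p is 60% or 30%. The hazard is constant from month d, with d = 0, or d = 3 or 6 to mimic the 3 to 6 months of prophylaxis in Group 2. Loss is independent of the event, at constant rate, reaching q = 10% or 20% by month 12.

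**1. Event-only mean against event-free time.** With W = 12 − d and λ = −ln(1 − p)/W:

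- event-only mean = d + 1/λ − W(1 − p)/p
- mean event-free time to month 12 = d + p/λ

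For d = 0 and p = 0.6, λ = 0.0764 and 1/λ = 13.10, so the event-only mean is 13.10 − 12 × 0.4/0.6 = 5.10 and event-free time is 0.6 × 13.10 = 7.86. For p = 0.3, 1/λ = 33.64, which gives 33.64 − 28 = 5.64 and 0.3 × 33.64 = 10.09.

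| d (months) | Event-only mean, 60% / 30% | Shift | Event-free time, 60% / 30% | Shift |
|---|---|---|---|---|
| 0 | 5.10 / 5.64 | 0.5 | 7.86 / 10.09 | 2.2 |
| 3 | 6.82 / 7.23 | 0.4 | 8.89 / 10.57 | 1.7 |
| 6 | 8.55 / 8.82 | 0.3 | 9.93 / 11.05 | 1.1 |

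**2. Crude incidence under loss.** With a = −ln(1 − p) and b = −ln(1 − q) × W/12:

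crude = (1 − q)^(d/12) × a/(a + b) × (1 − e^−(a+b))

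For d = 0, p = 0.6 and q = 0.2: a = 0.916, b = 0.223, so crude = 0.804 × 0.680 = 0.547.

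| d | True 60%, q = 20% | True 30%, q = 20% | Ratio (true 0.50) |
|---|---|---|---|
| 0 | 54.7% | 27.1% | 0.495 |
| 3 | 52.9% | 26.3% | 0.496 |
| 6 | 51.2% | 25.5% | 0.497 |

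At q = 10%, d = 0 and a true 60%, crude incidence is 57.4%, or 2.6 points low. The shortfall over the cases shown therefore runs from about 3 to 9 points.

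**3. Against sampling error.** The SAP plans about 150 patients, at least 15% of them in Group 3, and 2:1 allocation in Groups 1 and 2. That leaves at most 150 × 0.85/3 = 42.5, about 42, placebo patients, and fewer in the mITT Population. At 60% risk the 95% half-width is 1.96 × √(0.6 × 0.4/42) = 14.8 points pooled, or about 21 points with 21 placebo patients in each group.

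**4. Duration (assumed test results).** Appendix A shows weekly PCR columns for preemptive patients, institutional timing for prophylactic patients, and visits at months 3, 6, 9 and 12. Suppose results are positive on Days 21, 28 and 35 and negative on Day 42. The run is then 3 days (sampled days only), 35 − 21 = 14, 15 (inclusive), or 42 − 21 = 21 (to first negative). At 3-monthly visits, one positive near Day 183 and a negative near Day 274 give 1 day or 274 − 183 = 91 days.

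**The case against.** The strongest reply is that every 'time to' endpoint in section 3.4.2 is paired with incidence, so a reader sees prevention there. In the example, a 30-point difference in incidence would be printed next to the half-month shift in the mean. This stands. A reader might infer that the plan would hide a vaccine effect, or bias the comparison of arms. The SAP does not support either: incidence is reported, and with equal loss the risk ratio is almost unbiased.

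Second, the study is descriptive, without formal testing (section 3.1.4), and the bias is smaller than the sampling error. This also stands and limits the weight. It does not remove the point, because Kaplan-Meier and cumulative incidence are themselves descriptive and cost almost nothing.

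Third, a descriptive summary could include Kaplan-Meier, and section 5 leaves detailed programming specifications to another document. That is possible for day-counting conventions. Censoring is a matter of statistical method and belongs in the SAP, whose general rules point to non-missing values as observed.

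Fourth, the infection time in section 3.4.2.1 concerns any local PCR result above LLOQ, whereas Phase 3 planning concerns clinically significant infection. This is correct; the fix should therefore cover each endpoint in section 3.4.2, and that one above all.

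A reader might also infer that limiting duration to the first run, while anti-viral days are totalled, is a contradiction. It is not. These are different endpoints, first-run duration is legitimate, and recurrence is partly reflected in the number of anti-viral courses and total anti-viral days.

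**Conclusion.** The point holds for the 'time to' endpoints. As written, the plan produces event-only times and a crude incidence that understates the 12-month risk wherever patients withdraw or are lost.

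Under the assumed risks and loss rates, halving the risk moves the event-only mean by 0.3 to 0.5 months, against 1.1 to 2.2 months of event-free time. A true 60% risk reads about 3 to 9 points low at 10% to 20% loss. With equal loss the risk ratio stays at 0.495 to 0.497 against 0.50. The absolute bias is within a sampling error of about 15 points or more.

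This is therefore a cheap improvement to secondary, descriptive outputs that should be made, and not a threat to the study's primary conclusions. The duration rule is a minor clarification only: PCR results do not exist on consecutive days, so the wording allows several counts from the same results.

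**What to change.** In section 3.4.2, summarise each 'time to' endpoint, above all clinically significant CMV infection, by Kaplan-Meier. Alternatively use cumulative incidence, with death as a competing event, and graft loss too where the sponsor specifies that it precludes the event. Censor at the last PCR for infection and at the last assessment for the other events. Give 12-month estimates with 95% CI by arm within Groups 1 and 2.

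In section 3.4.2.1, state one end-date convention for duration above LLOQ and a rule for runs still open at the last sample, and report that the result depends on the testing interval. No convention is free of this: ending at the first negative result can turn one positive at 3-monthly visits into about 91 days. Total duration over all episodes is an optional addition.

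The cost is SAP wording before database lock and standard SAS procedures, with no new data. The small downside is that intervals will be wide and censoring is assumed non-informative.

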Record adverse events Record adverse events -Adverse events, regardless of causality, should be recorded up through 30 days after the last injection of study drug. -Adverse events considered related to the study drug should be recorded from 31 days after the last injection of study drug up through the End of Study Visit.	<-----X-----> Ongoing during study				<-----X-----> Ongoing during study			
Record SAEs	<-----X-----> Ongoing during study				<-----X-----> Ongoing during study			
Concomitant medications related to SAEs	<-----X-----> Ongoing during study				<-----X-----> Ongoing during study			
Concomitant medications of special interest -Anti-virals and immunosuppressants, non-study vaccines, granulocyte colony-stimulating factor, erythropoietin, and transfusions of blood product taken 7 days prior to and after transplant.	<-----X-----> Ongoing during study				<-----X-----> Ongoing during study			
Record adverse events of special interest:	<-----X-----> Ongoing during study				<-----X-----> Ongoing during study			
Graft rejection assessments	Transplant Follow-up visits per institutional standard.							X

CMV disease and syndrome assessments	Transplant Follow-up visits per institutional standard.							X
Blood sample for CMV PCR local testing: ⁶								
Patients to be followed preemptively post-transplant for the first 16 weeks after transplant.	X	X	X	X	X	X	X	X
Patients to be treated prophylactically with anti-virals post-transplant.	Time points following institution's standard of care.				X	X	X	X
Blood sample for central CMV PCR analysis	Study site personnel will draw the patient's blood sample for central CMV PCR analysis when local CMV PCR testing is conducted at the institution.				X	X	X	X

1. Time window of follow-up visits after transplant is ± 7 days.
2. Follow-up visits will occur per institutional standards of post-transplant clinical monitoring after discussion with the sponsor.
3. Per Section 6.4, the End of Study Visit is also the 12 months post-transplant follow-up visit.
4. During the study, it is possible that the time windows of study visits and assessments will be redundant. If time window is ± 2 weeks, assessments should NOT be duplicated.
5. There is a ± 7 day window on assessments during the post-transplant Follow-Up Period, to take into account public or religious holidays or weather, if not explicitly specified otherwise.
6. Only 1 post-transplant CMV management strategy will be followed (preemptively or prophylactically).

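### Duration of CMV DNAemia counts days with a positive result, but PCR is weekly at most on the fixed schedule; the value falls short by about one test interval and open episodes are not censored

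*SAP*

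**What the plan says.** SAP Section 3.4.2 lists among the secondary endpoints "Incidence and time to quantifiable CMV DNAemia, peak CMV DNAemia level, and duration of CMV DNAemia above the limit of quantitation", summarised descriptively in the mITT Population. Section 3.4.2.1 gives the rule: "Duration above LLOQ is the number of consecutive days with a quantifiable result above LLOQ, starting with the first such value". The rule does not name the PCR series. The infection definition in the same list does: "CMV infection is defined as quantifiable local CMV PCR test results above the lower limit of quantification (LLOQ").

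The post-transplant table in Appendix A sets the test times:

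- "Patients to be followed preemptively post-transplant for the first 16 weeks after transplant" have a test in each of Weeks 1 to 4 of the monthly block, and again at months 3, 6, 9 and End of Study.
- "Patients to be treated prophylactically with anti-virals post-transplant" have the same four later visits. Between them, testing follows institutional practice.
- Central PCR samples are drawn when local PCR is done and at the four later visits, so they fill no gaps.
- Note 5 allows a ±7 "day window on assessments during the post-transplant Follow-Up Period".

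Follow-up can stop before 12 months, for example "If the patient experiences graft failure requiring removal of the transplanted organ or returns to dialysis" (Section 2.2.1), or through withdrawal, loss to follow-up or death. Section 3.1.5 presents efficacy data as observed, without imputation. Section 3.1.3 summarises continuous variables by "arithmetic mean, standard deviation, median, minimum, and maximum values as descriptive statistics".

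**The concern.** The rule counts days that carry a result, but the fixed schedule produces no results on adjacent days. Its value therefore depends on how often the patient was tested as well as on how long the DNAemia lasted. The word consecutive implies that a run stops at a non-quantifiable result. The rule does not say which date closes the run: the last positive, the first negative or a point between them. Nor does it cover a patient who is still above LLOQ at the last sample.

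Mitigating DNAemia is the stated efficacy aim for preemptively managed seronegative recipients (Section 2.1.2). Section 2.2.4 says that the study should help provide point estimates of clinical efficacy endpoints for the design of Phase 3 trials. A duration that is too short by an amount set by test frequency is a poor estimate for that use. It also makes preemptive and prophylactic patients hard to compare.

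**Working it through.** The SAP gives no figure for this endpoint, so there is none to reproduce. The check applies the rule to an episode of known length.

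**Inputs.** The 7-day test interval comes from Appendix A (preemptive patients, first 16 weeks). About 91 days is the spacing of the month 3, 6, 9 and End of Study visits. The 14- and 30-day intervals, which stand for institutional testing, and all episode lengths are assumptions.

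**Formulas.** Take an episode of D days, tests every g days, and a uniformly random offset between onset and the first test. The mean number of positive tests is D/g. With n positives:

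- Literal reading (calendar days in a row that each have a positive result): 1 day whenever g exceeds 1.
- First to last positive, both days counted: (n − 1)g + 1. For D ≥ g the mean is D − g + 1.
- First positive to first later negative: n × g. For D ≥ g the mean is D.
- For D < g, the episode is detected with probability D/g. First-to-last then gives 1, and first-negative gives g.

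**Mean recorded duration (days)**

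| True D | Interval g | Literal | First to last | First negative |
|---|---|---|---|---|
| 21 | 7 | 1 | 21 − 7 + 1 = 15 | 21 |
| 21 | 14 | 1 | 21 − 14 + 1 = 8 | 21 |
| 35 | 7 | 1 | 29 | 35 |
| 35 | 14 | 1 | 22 | 35 |
| 35 | 30 | 1 | 6 | 35 |
| 35 | 91 | 1 | 1 (38% detected, 35/91) | 91 |

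For D ≥ g, first-to-last falls short by g − 1 days, that is by one interval less a day. One true length of 35 days is recorded as anything from 29 days down to 1, according to the test interval.

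**Arm contrast, both arms tested weekly, true 28 versus 14 days (ratio 0.50).**

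- First-to-last: 28 − 7 + 1 = 22 versus 14 − 7 + 1 = 8. The difference stays at 14 days, but the ratio is 8/22 = 0.36.
- First-negative: 28 versus 14, ratio 0.50.

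**One episode across the end of weekly testing.** Take tests on days 7, 14, …, 112 and then day 182, with DNAemia from day 85 to day 120 (35 days) and no institutional test in between. The first positive is on day 91, the last on day 112 and the next test on day 182.

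- Literal: 1 day.
- First-to-last: 112 − 91 + 1 = 22 days.
- First-negative: 182 − 91 = 91 days.

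**Open episode.** If this patient left the study after day 112, first-to-last would still record 22 days as a completed duration, although no negative result was ever seen.

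**The case against.** The strongest defence is that a programmer would not apply the literal reading. The wording points to the first unbroken run of positives, stopped by a non-quantifiable result, so only the closing-date convention is missing. The as-observed rule in Section 3.1.5 favours observed dates, and Section 5 leaves detail to a separate programming specification. The study is descriptive (Section 3.1.4), and this is one component of one of five secondary bullets.

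Much of this stands. The 1-day result shows that the wording does not fit the schedule; it does not predict what will be reported. However, Section 3.1.5 does not say how untested days count or what happens to open episodes. Section 3.4.2.1 does not refer this endpoint to the programming specification. The likelier reading still gives a value that is short by about one interval.

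A reader might go further and infer that the HB-101 versus placebo comparison is biased. The document does not support that. Groups 1 and 2 are each randomised 2:1, so test frequency should be roughly balanced between arms, within each group and when pooled. For episodes at least one interval long, the absolute difference survives.

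A reader might also take the widest gaps, such as 22 against 91 days, as typical. They assume that no institutional testing takes place between fixed visits, whereas the SAP provides for such testing. How dense it will be is not stated.

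**Conclusion.** The point holds and should be corrected before database lock. The rule does not fit the trial's own test schedule. On its likelier reading it understates episodes at least one test interval long by about one interval: 15 days for a true 21 with weekly tests, 8 with fortnightly tests. Ratios between arms are distorted (0.36 for a true 0.50 at 28 versus 14 days, tested weekly), and open episodes are treated as finished.

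The distortion lies in the level, the ratio and comparisons between preemptive and prophylactic patients. It does not touch incidence or time to infection, and no hypothesis test depends on it. The figures rest on assumed episode lengths, regular test intervals and a random onset relative to the tests. The document does not show how many patients will still be above LLOQ at their last sample. Its early-exit rules make such patients possible.

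**What to change.** Replace the rule in Section 3.4.2.1 along these lines:

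- Duration of the first episode runs from the date of the first local PCR result above LLOQ to the date of the first later local PCR result not above LLOQ.
- If the patient is still above LLOQ at the last PCR sample, censor the duration on that date.
- Summarise with a Kaplan-Meier median and report the number censored. The Section 3.1.3 mean has no proper value when some durations are open.
- Present durations separately for preemptive and prophylactic patients, as well as pooled.
- As a sensitivity analysis, repeat with the last positive date as the end.

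The cost is SAP wording and programming; no new samples or visits are needed. There are two downsides. Detected episodes shorter than the test interval are overstated: a true 5 days tested weekly is recorded as 7, and 1 − 5/7 = 29% of such episodes are missed under any rule. Durations also stay imprecise where tests are far apart, as the 91-day value for a 35-day episode shows. Showing the last-positive result beside the main one makes that imprecision visible.

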2.3 Study Endpoints

2.3.1 *Primary Endpoints*

For objective of assessing the safety and reactogenicity of HB-101, the primary endpoints are

- Incidence and severity of Adverse events (AEs), serious adverse events (SAEs), and changes in laboratory values
- Incidence and severity of localized or generalized injection site reactions

For objective of assessing the immunogenicity of HB-101, the primary endpoints are descriptive central statistics of the following immunogenicity parameters:

- CMV Neutralization (neut)
- CMV Enzyme-linked immunospot (ELISPOT) phosphoprotein 65 Kd (pp65)
- CMV ELISPOT gB

2.3.2 *Secondary Efficacy Endpoints*

- Incidence and time to clinically significant CMV infection, CMV disease, and CMV syndrome after transplant
- Incidence and time to CMV viremia requiring anti-viral therapy after transplant
- Incidence and duration (in days) of anti-CMV therapy courses (at therapeutic doses) required after transplant
- Incidence and time to quantifiable CMV DNAemia , peak CMV DNAemia level, and duration of CMV DNAemia above the limit of quantitation after transplant
- Incidence and time to graft failure and organ rejection after transplant

2.3.3 *Exploratory Efficacy Endpoints*

Descriptive central statistics of the following immunogenicity parameters:

- CMV Intracellular cytokine staining (ICS) pp65
- CMV ICS gB
- LCMV ELISPOT nucleoprotein (NP)

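### The course-count rule omits the flag, the trigger and the therapeutic-dose condition and counts CRF entries, so as written prophylaxis and split records become treatment courses

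*SAP*

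**What the plan says.** The endpoint list in SAP Section 2.3.2 reads "Incidence and duration (in days) of anti-CMV therapy courses (at therapeutic doses) required after transplant", and Section 3.4.2 repeats it. The secondary objective for seronegative recipients managed prophylactically (Section 2.1.2) likewise concerns anti-virals given at treatment dose. The lead sentence of Section 3.4.2 adds a count: "The incidence, duration, and number of courses of CMV anti-viral therapy through 12 months after transplant will be summarized descriptively for the mITT Population".

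Section 3.4.2.1 then gives four rules:

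- Use: "Anti-viral therapy use is defined as the recorded use of flagged anti-viral therapies on the concomitant medication CRF following the triggered start of anti-virals", the trigger being the start entered on the local CMV PCR form.
- Time: "Time to anti-viral therapy use is defined as the date of the first post-transplant anti-viral use – transplant date".
- Duration: "Duration of anti-viral therapy use is the total number of days of recorded post-transplant anti-viral use".
- Courses: "Number of anti-viral therapy courses is the sum of unique recorded post-transplant anti-viral entries on the concomitant medication CRF".

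Section 2.2.1 has Group 2 on prophylaxis for 3 to 6 months after transplant and allows prophylactic care in Group 3. The post-transplant schedule in Appendix A has anti-virals recorded as concomitant medications of special interest and does not limit them to treatment.

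**The concern.** The endpoint concerns courses of treatment, but the course rule counts anti-viral entries of any kind. Prophylaxis is planned for all of Group 2 and is among the drugs the CRF collects, so the rule takes it in. The patients most affected are those for whom the SAP sets the objective of reducing treatment-dose use. If the rule is followed, the number of courses reported for them is partly a count of prophylaxis records.

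There is a second, separate fault. An entry on a medication form is not a course. One treatment may be entered on several lines, and the same drug may be used for two separate treatments. The SAP neither says what *unique* means nor how consecutive entries are joined. This fault also reaches Group 1, where planned prophylaxis is not the issue.

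**Working it through.** The SAP gives no figure for this endpoint, so there is nothing to reproduce. The check sets the four rules against the endpoint and then scores example patients.

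**Step 1: conditions stated in each rule of Section 3.4.2.1.**

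| Rule | Flag | Trigger | Therapeutic dose | Reuses the term defined in the use rule |
|---|---|---|---|---|
| Use | yes | yes | no | defines it |
| Time | no | no | no | yes |
| Duration | no | no | no | yes |
| Courses | no | no | no | no; it names its own source, the CRF entries |

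The dose condition appears in the endpoint lists but in none of the four rules. *Flagged* is not explained, so it cannot be assumed to separate treatment from prophylaxis.

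**Step 2: how many patients it could reach.** Inputs: about 150 patients (Section 2.2.4), Group 2 at most 54% and randomised 2:1 (Section 2.2.1). 0.54 × 150 = 81, that is 54 on HB-101 and 27 on placebo. This is an enrolment ceiling. The mITT Population will be no larger, since it needs a transplant and at least 2 doses. Prophylactically managed Group 3 patients come on top; the SAP gives no number for them.

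**Step 3: a never-treated prophylaxis patient.** With prophylaxis on at least one CRF line, the course rule gives at least 1. A treatment-only rule gives 0. No event rate has to be assumed.

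**Step 4: a patient with two treatments.** Constructed example: one prophylaxis record completed before any trigger, a first treatment entered as two records, a second treatment in one record, all with the same drug. The true number of treatment courses is 2.

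- *Unique* as distinct records: 1 + 2 + 1 = 4.
- *Unique* as distinct drugs: 1.
- Trigger carried over, distinct records: 2 + 1 = 3.
- Trigger carried over, distinct drugs: 1.

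None of these gives 2. Adding the trigger removes the prophylaxis record but does not turn entries into courses.

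**Step 5: duration.** Take 3 to 6 months as 90 to 180 days. For the never-treated patient of Step 3, the literal wording gives 90 to 180 days. If the conditions are inherited from the defined term, the result is 0 treatment days. Both readings are open on the text. Under the inherited reading, prophylactic-dose drug taken after a trigger could still count unless the flag excludes it, which the SAP does not say.

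**Step 6: time.** Section 3.4.2 also lists time to CMV viremia requiring anti-viral therapy. The only rule in Section 3.4.2.1 that times the start of therapy is the time rule. If it is used for that endpoint and read literally, it would date the start of prophylaxis in Group 2.

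**The case against.** The strongest reply is that the conditions are inherited. Section 3.4.2.1 defines anti-viral therapy use with flag and trigger, and the time and duration rules follow directly under that label. This stands. A reader might infer that duration and time are wrong in the same way as the count; the text does not support that, only that they are open to two readings. The reply is much weaker for the course rule, which does not reuse the term and names its own source. Even if granted, it leaves split entries and the dose condition unresolved.

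The number of courses is not in the endpoint list of Section 2.3.2. It appears only in the lead sentence of Section 3.4.2. That is correct and limits the weight of the point, but the summary is planned and the SAP defines how to derive it.

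The CRF is not shown, and Section 5 leaves detailed programming specifications to a separate document. Those may settle what *flagged* and *unique* mean. They cannot properly reverse a counting rule that the SAP states.

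Section 3.4.2 also plans a table of anti-viral therapy use "for all post-transplant patients regardless of dose of medications". A reader might take it as a further affected output. It uses the defined term, so the documents do not show that prophylaxis before a trigger enters it.

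Finally, one might want to state how far the error would dilute a difference between arms. That would need treatment rates, treatment lengths and a vaccine effect that the SAP does not give, and the SAP plans no ratio or standard error of an arm difference for these endpoints. No such figure is offered here.

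**Conclusion.** The course-count rule is wrong as written and should be corrected before database lock. A never-treated prophylaxis patient scores at least 1 instead of 0, and a treatment entered on k distinct records scores k if *unique* means records. If it means drugs, repeat treatment with one drug scores 1. The first result assumes only that prophylaxis is entered on the concomitant medication CRF, as Appendix A indicates. The 4-or-1 result for a patient with 2 courses is a constructed example, not an expected frequency.

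The duration and time rules need clarification, not correction.

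The reach is narrow: descriptive secondary summaries in a study without formal hypothesis testing (Section 3.1.4). Section 4.1 would carry the same derivations into any interim analysis. A reader might infer that the incidence of anti-viral therapy or the main conclusions are compromised. The documents do not support this: incidence rests on the trigger and is not affected by prophylaxis given before it, and the primary safety and immunogenicity endpoints do not use these rules.

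**What to change.** In Section 3.4.2.1:

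1. Restrict the course count, and explicitly the duration and time rules, to days of flagged anti-viral use at treatment dose, as recorded on the CRF, on or after the triggered start.
2. Where a record began before the trigger, count its treatment portion from the trigger onward. Keeping only records that start on or after the trigger would lose drug begun earlier and continued at treatment dose.
3. State what *flagged* means and whether it separates treatment from prophylaxis.
4. Replace the count of unique entries with a course defined as a continuous treatment period. Join contiguous or overlapping records under a gap rule fixed in advance, and count each calendar day once.
5. Say whether the time rule serves the endpoint on viremia requiring therapy.

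Stating how untreated patients are scored, whether a drug switch opens a new course, and that prophylaxis is summarised separately would help, but these are additions and do not correct an error.

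The cost is minor SAP wording and derivation programming, with no new patients or procedures. It depends on treatment use being identifiable on the concomitant medication CRF. If it is not, the SAP should say so and rename the summary to what is actually counted.
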